Statistical approach: In terms of statistical approach, this is a superiority trial in which we seek to verify our central study hypothesis that provision of booster vaccine messaging will result in greater acceptance and uptake of the booster vaccine. Following the recommendations of Hussey and Hughes, our statistical analyses will focus on comparing the vaccine uptake rates during the time periods when booster vaccine messaging is in place (Intervention M) and when the system is not in place (Control - usual care) using mixed effects logistic models. The outcome of interest is the binary indicators of whether they have received a booster vaccine in the ED (uptake - yes/no). Models will include a normally distributed random center effect (on the logit scale) to accommodate potential within-center characteristics (e.g., case mix, demographics), as well as terms for time and intervention. Hypotheses testing will focus on the statistical significance of the intervention indicator. We will fit the mixed effects models using maximum likelihood and routines in Stata.

We will test our primary hypotheses and analyze outcomes according to the study arm (index visit in Intervention M day versus control day) to which patients were allocated, regardless of whether they received booster vaccine messaging or not - *intention to treat analysis*.

In addition to the effects on *total* vaccine acceptance, we will also examine the effect of booster vaccine messaging on acceptance in patient sub-groups, especially African American and Latinx persons. Booster vaccine messaging may work for one patient sub-group and not others -- these additional analyses will guide future directions and modifications of booster vaccine messaging.

XVI. Data Management Plan

We will manage data using REDCap, hosted by the core site (UCSF) for secure data entry and management. Patient identifiers (medical record numbers and phone numbers) only link will be

to unique study ID numbers, which will be housed in files that are kept separate from other study data. We will develop a detailed data dictionary to ensure consistent standards across sites. We will reduce missing or erroneous data using the REDcap data quality tool.

XVII. Sample Size Considerations

The sample size calculations for this research are governed by hypothesis testing of Specific Aim I -- Implementation of booster messaging platforms will be associated with increased booster vaccine uptake (primary outcome) in unvaccinated ED patients. Considering the high benefit of increasing vaccine uptake and the negligible risk of the intervention (a trusted messaging program), even a small effect size of increased uptake would be a clinically important difference. By investigator consensus, we have determined that the intervention would be clinically useful if it increased booster vaccine uptake by 7%.

We base the sample size calculation on the comparison of the proportion of patients who accept the vaccine between the Intervention M and Control time periods using standard formulae for individual randomization. We have verified that these sample sizes are conservative by simulation of data using a mixed random effects model. Our baseline level of vaccine uptake in the control arm is estimated to be approximately 5%. With this uptake level we find that at an alpha=0.05 level and a power of at least 0.80, we will need to enroll 744 participants (248 in each arm) in the study to detect the difference of interest (a setting in which the vaccine uptake rate will increase by 7% during Intervention periods vs Control periods).

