Recognizing the ED as a unique opportunity to address COVID-19 booster vaccine hesitancy in underserved populations, we will launch the PROmotion of COVID-19 BOOSTer VA(X)ccination in the Emergency Department (PROBOOSTVAXED) trial as an extension of the PROCOVAXED trial, seeking to increase COVID-19 booster vaccine acceptance and uptake among vaccinated ED patients. Because of Omicron variant-associated surges during the COVID-19 pandemic with corresponding research staff illness and ED overcrowding, we found

wide week-to-week fluctuations in enrollment in the PROCOVAXED study. To reduce this variability of enrollment, we have changed the unit of randomization from 1-week to 1-day in the PROBOOSTVAXED trial.

IMPORTANT CHANGE: Under intense political pressure and in response to Congress' reluctance to spend more on COVID-19 pandemic relief, the Biden administration recently made two announcements: 1) the national public health emergency declaration regarding the COVID-19 pandemic will be left to expire as of January 11, 2023, and 2) the administration will end their provision of free COVID-19 vaccines, testing and therapeutics, shifting the costs for vaccines, testing and treatments to health insurers and patients via commercial payment mechanisms. Because of these changes in reimbursement, we have been informed that only some of the PROBOOSTVAXED study sites will have COVID-19 vaccines available for distribution in the ED, whereas others will not. Nevertheless, we will proceed with the same research protocol, however, we will be performing additional subgroup analyses that compare 30-day vaccine uptake in sites with available COVID-19 vaccine to those without for the intervention and control arms.

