Sites will be assigned be assigned to a condition for a day. Randomization within each of the site uses pseudorandom number to permute blocks of time. The blocks consist of 15 days duration during which each condition appears for 5 days. Hence, in any 15 day period there will be a balance of interventions within each of the sites. The particular days of each week (Monday, Tuesday, Wednesday, Thursday and Friday) for each of the study arms will thus vary randomly. This randomization scheme will minimize secular trends (changes in perceptions about the booster vaccine that may occur through the course of various pandemic waves). We

will generate a full study calendar based on this randomization scheme. To try to maintain masking of allocation, sites will be given a blacked-out study calendar and will be instructed to open the calendar for a particular study day the morning of that study day (other than that study day, the rest of the calendar will remain blacked out).

VI. Site Orientation and Training

The Core UCSF Site will develop orientation materials to familiarize the ED Sites with the study protocol. Each site will employ one or more Clinical Research Coordinators (CRCs), who will report to the Site PI and be responsible for day-to-day study implementation. We will develop and disseminate a manual of operating procedures (MOP) with standard personnel training methods, including education kits with scripts, summary cards, and PowerPoint presentations to assist coordinators in the orientation of site clinicians and other staff to our study protocol. We will convene ZOOM conference calls to review this summary and develop plans for optimization of PROBOOSTVAXED messaging platforms to improve usability and workflow. We will refine procedures with updates delivered to the site PIs during weekly ZOOM conferences.

VII. Study Hotline and Quality Assurance

We will maintain a study hotline and encourage study personnel to contact the PI and Central Study Coordinator for all issues and queries. Hotline hours will be during primary study hours (weekday 8 a.m. to 5 p.m. PST).

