CRCs will keep a running log of all study flow and enrollment, recording the following data for all patients approached: study date, study arm, "Yes" and "No" agreeing to surveys, delivery or non-receipt of messaging platforms, agreeing to receipt of study vaccines, ED vaccine availability, receipt of vaccines in the ED, "Yes" and "No" agreeing to follow-up calls and EHR review. See Master Data Flow.

XV. Data Analysis Analysis for Specific Aim I

The primary study comparison is uptake (receipt) of a booster vaccine at any vaccination location within 30 days of the index ED visit, comparing participants seen on Intervention M dates with those seen on Control (No Messaging, No Vaccine Acceptance Question) dates to test our study hypothesis: *Implementation of PROBOOSTVAXED trusted messaging platforms in EDs will be associated with increased booster vaccine uptake in vaccinated ED patients*. This outcome will be ascertained by either review of a participant's EHR 30 days after their index ED visit or a follow-up phone call.

There are three secondary comparisons for Specific Aim I:

- 1) Comparison of 30-day booster vaccine uptake between the Intervention M and Intervention Q arms
- 2) Receipt of a booster vaccine during the index ED visit, comparing participants seen on Intervention M dates with those seen on Control dates - ascertained by check of the participant's EHR on the day after their ED visit

Outcomes will be compared using mixed logistic regression with a fixed effect for randomization assignment, a normally distributed random effect to allow for clustering by enrolling center, and restricted cubic splines to allow for secular trends during the study period. The treatment effects

will be tested by the coefficient for the fixed effect of study arm along with 95% confidence intervals.

Analysis for Specific Aim II

For Specific Aim II, we will compare outcomes in participants seen on Intervention M arm dates with those seen on Intervention Q arm dates to test our study hypothesis: *Implementation of PROBOOSTVAXED trusted messaging platforms in EDs will be associated with increased booster vaccine acceptance in vaccinated ED patients.*

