The outcome is booster vaccine acceptance (defined as a response of "yes" to the question "Would you accept the booster vaccine in the emergency department today if your doctor asked you?"). This outcome will be compared using mixed logistic regression with a fixed effect for randomization assignment, a normally distributed random effect to allow for clustering by enrolling center, and restricted cubic splines to allow for secular trends during the study period. The treatment effects will be tested by the coefficient for the fixed effect of study arm along with 95% confidence intervals.

Analysis for Specific Aim III

For Specific Aim III, the outcome is uptake (receipt) of a booster vaccine at any vaccination location within 30 days of the index ED visit. We will compare outcomes in participants seen on Intervention Q arm dates with those seen on Control dates to test our study hypothesis: Implementation of an ED protocol in which patients are asked whether they will accept a booster vaccine (and notifying ED providers when they say they will accept it) will be associated with increased booster vaccine uptake in vaccinated ED patients.

A secondary outcome for Specific Aim III is receipt of a booster vaccine during the index ED visit, comparing participants seen on Intervention Q dates with those seen on Control dates - ascertained by check of the participant's EHR on the day after their ED visit.

Subgroup Analyses

Another focus of this research is on ED patients who lack primary care group, defined on the Intake survey question: "Do you have a regular clinic or doctor for medical care?" We will analyze outcomes according to the binary indicator of having primary care – yes versus no (and unsure).

We will additionally stratify outcomes by study site (representing different regions of the country and different communities), vaccine administration capability, age, gender, primary language, and race/ethnicity.

Subgroups will be tested by adding a subgroup by intervention interaction to the mixed logistic regression. A subgroup will be considered significant if the pairwise intervention by subgroup omnibus test is significant at the 0.05 level.

Rationale for time (1-day unit) cluster and consideration of Alternative Study Designs:

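### Days are permuted to arms in 15-day blocks within each site, but no written model carries the site-by-block stratum; with clearly uneven enrolment the Aim II interval can be modestly too narrow

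*Combined protocol and SAP*

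**What the plan says.** Section V (Randomization) makes the site-day the allocated unit: "Sites will be assigned be assigned to a condition for a day". It permutes within site: "Randomization within each of the site uses pseudorandom number to permute blocks of time". It fixes the block: "The blocks consist of 15 days duration during which each condition appears for 5 days". The stated result is that "in any 15 day period there will be a balance of interventions within each of the sites". The randomisation stratum is therefore site by 15-day block.

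Section XV (Data Analysis) gives the Aim I model: "Outcomes will be compared using mixed logistic regression with a fixed effect for randomization assignment". Aims I and II share the remaining terms: a "normally distributed random effect to allow for clustering by enrolling center, and restricted cubic splines to allow for secular trends". The paragraph on statistical approach repeats a random center effect with terms for time and intervention. The subgroup models add only a subgroup-by-intervention interaction, and Aim III has no model of its own. No model contains a site-specific time curve, a block term, a site-day term or a robust variance.

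On enrolment, section VIII describes a convenience sample with no daily quota. The study Overview reports "wide week-to-week fluctuations in enrollment in the PROCOVAXED study" and gives reducing that variability as the reason for moving to a 1-day unit.

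**The concern.** A center effect removes stable differences between sites, and a common spline removes a trend shared by all of them. Neither removes changes over time that differ between sites, such as local waves or news in four cities. Section V itself gives shifting perceptions over pandemic waves as a reason for the blocks.

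Each site-block has five days per arm, but nothing fixes the number of participants per day. If M and Q participant numbers differ within a site-block, the unmodelled level of that site-block enters the M versus Q contrast, and the model's standard error does not count it. Aim II is the most exposed, because acceptance is probably near the middle of the scale and has its own primary outcome. At stake is whether the Aim II interval has its nominal coverage.

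**Working it through.** **The plan's own figure.** Section XVII: 5% versus 12%, alpha 0.05 (two-sided assumed), power 0.80, mean proportion 0.085.

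n per arm = [1.96 × √(2 × 0.085 × 0.915) + 0.842 × √(0.05 × 0.95 + 0.12 × 0.88)]² / 0.07² = 248, and 3 × 248 = 744.

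This reproduces exactly and is not affected by the present point. The plan gives no sample size or power for Aim II; M versus Q has 2 × 248 = 496 participants.

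**Inputs for Aim II**
- Five sites (section IV). Taking 15 September 2023 to 28 February 2024 gives 119 weekdays, and 119/15 = 7.9, so about 8 blocks per site.
- M and Q days: 5 × 8 × 10 = 400, so m = 496/400 = 1.24 participants per day.
- Acceptance 43% (assumed), from the 57% hesitant in the earlier survey described in the study Overview: 100 − 57.
- Site-by-block SD σ (logit scale) and day-level coefficient of variation (CV) of the enrolment rate, on top of Poisson variation: assumed, because the documents give neither.

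**Hand check of the mechanism.** Let d be the M-minus-Q difference in participants in a site-block, and let N = 496. To first order,

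true variance / model variance ≈ 1 + p(1−p)σ² × (Σd²/N − 1).

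With perfectly even enrolment d = 0 and the ratio is below 1. With Poisson enrolment Σd²/N averages 1 and the ratio is 1. With extra day-level variation Σd²/N averages 1 + m × CV², so the ratio is 1 + p(1−p)σ² × m × CV². Here p(1−p) = 0.43 × 0.57 = 0.245.
- σ = 0.5, CV = 1.4 (CV² = 2): 1 + 0.245 × 0.25 × 1.24 × 2 = 1.15, so model SE / true SD = 1/√1.15 = 0.93.
- σ = 0.8, CV = 2: 1 + 0.245 × 0.64 × 1.24 × 4 = 1.78, so 1/√1.78 = 0.75. This overstates the problem, because the approximation is rough at large σ and the center and time terms absorb part of the variation.

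**Simulation under no arm effect** (4,000 runs per cell, Monte Carlo error about 0.35 points). The written model was fitted with center indicators, arm and one 4-knot spline. The comparison adds a site-by-block random intercept.

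| Enrolment | σ = 0.5: SE/SD | Type I, written → with block term | σ = 0.8: SE/SD | Type I, written → with block term |
|---|---|---|---|---|
| Even | 1.01 | 4.9% → 5.2% | 1.04 | 4.5% → 5.3% |
| Poisson | 0.99 | 5.2% → 5.3% | 0.98 | 5.2% → 5.3% |
| CV 1.0 | 0.97 | 5.7% → 5.1% | 0.94 | 6.1% → 5.1% |
| CV 1.4 | 0.93 | 7.0% → 5.6% | 0.88 | 8.1% → 5.7% |
| CV 2.0 | 0.89 | 8.0% → 6.3% | 0.81 | 10.6% → 5.6% |

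With no site-block variation, the written model at CV 2.0 already gives 6.0%, so not all of the bottom row comes from the missing term.

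**Other forms of unevenness**
- Each site enrols on a quarter of its days (CV = √(0.75/0.25) = 1.7), 1,500 runs: 6.0%, 8.2% and 11.5% at σ = 0.4, 0.6 and 0.9; with the block term 5.7%, 6.5% and 5.4%. Repeat runs gave 7.9% and 11.0% at 0.6 and 0.9. A further rerun gave about 5% to 6.5% at 0.4 to 0.6 and 10% at 0.9.
- Half of days, σ = 0.6: 5.5%, and 6.5% in a repeat.
- Fluctuation by week: about 5% to 6% at a week-level CV of 1.0 (σ = 0.5 to 0.8) and 6.2% at 1.4 (σ = 0.6). If each site enrols in only one week of three, 6.6% (σ = 0.5) and 8.1% (σ = 0.8).

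**Uptake.** At 8% uptake, σ = 0.6, quarter of days: 6.0% written against 5.4% with the block term, with Monte Carlo error of about 0.6 points.

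**Variation at the site-day itself** (SD 0.5, no block variation): 5.7% to 8.2% under the written model and 5.7% to 7.8% with the block term. The block term does not cover the allocated unit.

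**The case against.** The strongest case against is that the inflation needs two conditions together, drift that differs by site and strongly uneven enrolment, and the documents establish neither. The fluctuation in the study Overview was week to week, in a trial randomised by week, and the 1-day unit was adopted to reduce it. A slow or busy block affects all arms alike. Section V plans a full weekday calendar, and each site sees 150 to 250 patients a day. A site-day cluster-robust variance without any block term also brings quarter-day type I error down, from 7.9% to 6.1% at SD 0.6 and from 11.0% to 6.0% at SD 0.9.

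Most of this stands. A reader might infer from the study Overview that 8% to 11% is the error to expect; the documents do not support that. Week-level unevenness is damped but not removed: in a five-day week of a 15-day block, M and Q have equal days with probability (1 + 250 + 500)/3003 = 25%, so they differ in 75% of weeks. Very uneven enrolment is also not implausible. The target is only 744/(5 × 119) = 1.25 participants per site-day, so a site enrolling five per active day would need only a quarter of its days.

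A reader might also infer that the odds ratio is biased toward 1, because the written model returned a log odds ratio of 0.475 to 0.48 where 0.50 was simulated. That is non-collapsibility: 0.50/√(1 + 0.346 × 0.6²) = 0.47 is about what a model not conditioning on the block should return, and the plan never names a block-conditional odds ratio as its target.

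Finally, a single time curve for all sites is the natural reading of "restricted cubic splines to allow for secular trends during the study period", but the plan does not say so in words.

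**Conclusion.** The point holds in a limited form. The stratum within which days are permuted is absent from every written model. For Aim II this leaves type I error at about 5% with even or Poisson enrolment and about 5.5% to 8% in moderately uneven scenarios. It reaches 10% to 11% only at an assumed site-by-block SD of 0.8 to 0.9 with enrolment on about a quarter of days or a day-level CV of 2. These ranges rest on an assumed SD, an assumed enrolment spread and a 43% acceptance rate borrowed from an earlier survey.

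It would be wrong to conclude that the primary comparison is compromised. The effect on uptake in Aims I and III is small and within simulation error, and the 744 is untouched.

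**What to change.** Carry the block number from the study calendar into the dataset. In section XV, add a random intercept for site by 15-day block to the mixed logistic models, keeping arm, center and the splines. State that Aim III uses the same model, and say whether the spline is common to all sites.

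Because this term does not cover variation at the allocated site-day, pair it with a site-day random intercept or a site-day cluster-robust variance. The nested form (center, site-block, site-day) is the simpler one to write. With a center random effect in the likelihood, site-days of one center are not independent contributions, so a site-day sandwich variance sits more naturally with center entered as indicators. The paired model was not simulated here.

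The cost is one derived variable, the added random-effect levels, and slightly wider intervals when such variation is present. If the added variances are estimated as zero, the random-intercept model reduces to the planned one. Writing it in advance avoids a choice made after seeing the enrolment pattern.

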The PROCOVAXED trial was a multicenter study that sought to decrease COVID-19 vaccine hesitancy and increase COVID-19 vaccine uptake through the use of vaccine messaging platforms in the emergency department (ED). In this trial, we found that implementation of our COVID-19 messaging platforms (videos, information sheets and scripted, direct messaging) were associated with greater COVID-19 vaccine acceptance and uptake among unvaccinated ED patients (Rodriguez RM, Nichol G, Eucker SA, et al. Effect of COVID-19 Vaccine Messaging Platforms in Emergency Departments on Vaccine Acceptance and Uptake: A Cluster Randomized Clinical Trial. *JAMA Intern Med.* 2023;183(2):115–123. doi:10.1001/jamainternmed.2022.5909).

In January 2022, we extended PROCOVAXED by shifting the focus to *vaccinated* ED patients to examine the timely and critically important topic of booster vaccine hesitancy in underserved ED populations. To better characterize COVID-19 booster hesitancy, we performed a crosssectional study at five high-volume, safety-net hospital EDs in four cities (San Francisco, Philadelphia, Seattle, and Durham, NC) using survey tools to gather quantitative data on vaccination status, demographic variables, usual source of care, and attitudes toward booster vaccination. Of 771 participants who had completed their full initial series, 316 (41%) had not received any booster vaccine. Among these 316 non-boosted participants, 179 (57%, 95% CI 51-62) stated they would decline or were unsure whether they would accept a booster vaccine if it was offered to them (i.e., booster-hesitant). We found the following associations with booster vaccine hesitancy: age 35-49 years vs age 18-34 years (OR 1.16, 95% CI 0.99-1.36); Asian vs White race (OR 0.21, 95% CI 0.05-0.93); Hispanic/Latino vs White ethnicity (OR 1.59, 95% CI 0.82-3.09); primary language non-English vs English (OR 2.35, 95% CI 1.49-3.71); and Republican vs Democrat party affiliation (OR 6.07, 95% CI 4.21-8.75). The three most common reasons for booster vaccine hesitancy were a preference to wait for more information (25%), concerns about side effects and safety (24%), and "I don't need one because I'm fully vaccinated" (20%).

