Specific Aim I: To determine whether implementation of COVID-19 booster vaccine trusted messaging platforms is associated with increased booster vaccine uptake in vaccinated ED patients. At five EDs (Zuckerberg San Francisco General, UCSF Parnassus Medical Center [San Francisco, CA], Thomas Jefferson University Hospital [Philadelphia, PA], Ben Taub Hospital [Houston, TX], Duke University Medical Center [Durham, NC]), we will conduct a cluster-randomized controlled trial of the implementation of PROBOOSTVAXED trusted messaging platforms, with 30-day booster vaccine uptake as the primary outcome and booster vaccine uptake in the ED as a secondary outcome. *Hypothesis: Implementation of PROBOOSTVAXED trusted messaging platforms in EDs will be associated with increased 30-day booster vaccine uptake in vaccinated ED patients.*

Specific Aim II: To determine whether implementation of COVID-19 booster vaccine trusted messaging platforms in EDs is associated with increased booster vaccine acceptance in vaccinated ED patients. For this specific aim, booster vaccine acceptance in the ED assessed via ED survey will be the primary outcome. *Hypothesis: Implementation of PROBOOSTVAXED trusted messaging platforms in EDs will be associated with increased booster vaccine acceptance in vaccinated ED patients*.

Specific Aim III: To determine whether implementation of a protocol in which ED patients are asked whether they will accept a COVID-19 booster vaccine in the ED is associated with increased booster vaccine uptake in vaccinated ED patients. Hypothesis: Implementation of an ED protocol in which patients are asked whether they will accept a COVID-19 booster vaccine will be associated with increased 30-day booster vaccine uptake in vaccinated ED patients.

General Design: This is a three-arm cluster-randomized controlled trial (CRCT) to accomplish Specific Aims I, II, and III.

Study arms

PROBOOSTVAXED Intervention M	Intervention Q (Vaccine Question,	Control (No Messaging, No
(Messaging + Vaccine Question)	No Messaging)	Vaccine Question)

- Vaccine messaging given
- Vaccine acceptance question asked
- No vaccine messaging
- Vaccine acceptance question asked
- No vaccine messaging
- No vaccine acceptance question

Primary Outcome for Specific Aims I and III: Booster Vaccine Uptake in the ED

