We will enact rigorous methods for clinical trial quality assurance and performance improvement, including: 1) systematic review of enrollment logs, 2) weekly audits of random samples of data for accuracy and missing elements, and 3) structured review of protocol deviations or violations. The Central Study Coordinator will prepare monthly summary report cards, tabulating individual site quality assurance metrics for review during scheduled Steering Committee calls. The overall study PI ([name]) will discuss site-specific data with site PIs individually and summarize these data collectively during Steering Committee calls, with prompt dissemination of plans for process improvement.

VIII. Recruitment, Inclusions, Exclusions, and Consent

Practical budget considerations and limits on research personnel in patient care areas during the COVID-19 pandemic, preclude 24/7 delivery of the PROBOOSTVAXED trusted messaging platforms and enrollment in this study. We will use a convenience sample technique to approach all eligible adult patients who present to our study EDs during 8-hour (one-day) blocks, typically beginning at approximately 9 a.m. and continuing to approximately 5 pm. Sites will be given leeway to vary their particular study time hours, as long as these study hours remain consistent from week to week.

Inclusions will be:

- 1) Age > 18 years
- 2) Presenting to ED
- 3) No receipt of COVID-19 booster within prior 6 months
- 4) Able to provide informed consent
- 5) Fluent in English or Spanish

6) Anticipated ability to complete study intervention in ED i.e., able to watch a 3-minute videoclip

Reviewing ED triage information, we will exclude patients with the following characteristics:

- 1) Major trauma such that it will preclude survey
- Inability to participate in a survey because of intoxication, altered mental status, or critical illness
- 3) Incarceration
- 4) Psychiatric hold
- 5) Patients who state that they have already received a bivalent COVID-19 booster vaccine or other COVID-19 vaccine within the prior 6 months
- 6) Patients who are in the ED for suspected acute COVID-19

[figure not shown]
NOTE: For all three study arms, study procedures should be performed in patient waiting times and not interfere or disrupt patient care in any way.

IX. Study Procedures: Intervention Blocks

Procedures and workflow during PROBOOSTVAXED Intervention M Study Arm

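### The written eligibility list does not require any earlier COVID-19 vaccination, although every aim concerns vaccinated ED patients

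*Combined protocol and SAP*

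**What the plan says.** **Intended population.** The Overview presents the trial as "seeking to increase COVID-19 booster vaccine acceptance and uptake among vaccinated ED patients". Aim I asks whether messaging "is associated with increased booster vaccine uptake in vaccinated ED patients", and Aims II and III name the same population. Section XV repeats it: the Aim I hypothesis is that "trusted messaging platforms in EDs will be associated with increased booster vaccine uptake in vaccinated ED patients", and the Aim III hypothesis is that asking the acceptance question "will be associated with increased booster vaccine uptake in vaccinated ED patients".

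**Eligibility.** Section VIII has six inclusions and six exclusions. Only two of the twelve concern COVID-19 vaccine history:
- Inclusion 3: "No receipt of COVID-19 booster within prior 6 months".
- Exclusion 5: "Patients who state that they have already received a bivalent COVID-19 booster vaccine or other COVID-19 vaccine within the prior 6 months".

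**Earlier studies.** The Overview survey that led to this trial did state a standard: "Of 771 participants who had completed their full initial series". The parent trial studied the opposite population and reported "greater COVID-19 vaccine acceptance and uptake among unvaccinated ED patients".

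**Sample size.** Section XVII states the governing Aim I hypothesis for unvaccinated ED patients, while still naming booster uptake as the outcome. It assumes about 5% uptake in the control arm, a 7-point increase, alpha 0.05 and power of at least 0.80, and arrives at 248 per arm, 744 in total.

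**The concern.** Both vaccine-history criteria are negative conditions. Someone who has never had a dose satisfies inclusion 3 and is not caught by exclusion 5. Section VIII has staff approach every eligible adult during study hours, so the list, and not the wording of the aims, decides who is enrolled.

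No later step in the documents separates such participants. The Statistical approach in Section XV analyses by allocated arm, and prior vaccination is not among the listed subgroups. The plan also does not say what vaccinated means (any dose, or a completed initial series), so five sites could apply different rules.

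At stake is the population that the result describes. If never-vaccinated patients were enrolled, the estimate would refer to a mix that no aim names. If they responded less to booster messaging, the overall effect would be diluted.

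**Working it through.** **1. The list against the aims.**

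| Criterion in Section VIII | Never-vaccinated adult |
|---|---|
| Inclusion 3 (no booster in the prior 6 months) | satisfied |
| Exclusion 5 (bivalent booster, or another COVID-19 vaccine in the prior 6 months) | not triggered |
| The other five inclusions and five exclusions | silent on vaccine history |

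Such a person meets the list but lies outside the population of Aims I, II and III.

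**2. The plan's sample size.** Inputs from Section XVII: p1 = 0.05, p2 = 0.05 + 0.07 = 0.12, alpha 0.05, power 0.80, formula for individual randomisation. The section does not state sidedness; two-sided reproduces its figure. With p̄ = (p1 + p2)/2 = 0.085:

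n = [1.960 × √(2p̄(1−p̄)) + 0.842 × √(p1(1−p1) + p2(1−p2))]² / (p2 − p1)²

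= [1.960 × √0.15555 + 0.842 × √0.1531]² / 0.0049 = 247.98 (computed with unrounded normal quantiles), so 248 per arm and 3 × 248 = 744. Power at 248 is 0.800 and the odds ratio is 2.59. The plan's figure reproduces, and the word unvaccinated does not enter it.

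**3. Illustration of dilution.** Let u be the never-vaccinated share. The documents give neither u nor uptake in that group, so all values below are assumptions. They also assume that 5% and 12% describe the vaccinated participants only. Each arm's rate is (1−u) × the vaccinated rate + u × the never-vaccinated rate, and

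power = Φ{[(p2 − p1)√n − 1.960√(2p̄(1−p̄))] / √(p1(1−p1) + p2(1−p2))}, with n = 248.

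| Assumed uptake in the never-vaccinated | u | Control vs messaging | Odds ratio | Power | n per arm for 80% |
|---|---|---|---|---|---|
| A: zero in both arms | 10% | 4.5% vs 10.8% | 2.57 | 0.753 | 279 |
| A | 20% | 4.0% vs 9.6% | 2.55 | 0.699 | 317 |
| B: 5% in both arms (no messaging effect) | 10% | 5.0% vs 11.3% | 2.42 | 0.728 | 295 |
| B | 20% | 5.0% vs 10.6% | 2.25 | 0.643 | 359 |
| C: same as the vaccinated in each arm | any | 5% vs 12% | 2.59 | 0.800 | 248 |

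Example, B at 20%: 0.8 × 12% + 0.2 × 5% = 9.6% + 1.0% = 10.6%. The largest loss shown is 0.800 − 0.643 = 0.157.

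**4. A vaccinated-only analysis of the same enrolment.** At 10%, 248 × 0.9 ≈ 223 per arm remain, and power at 5% vs 12% is 0.757. At 20%, 248 × 0.8 ≈ 198 remain, and power is 0.706. Change against the mixed analysis (differences taken before rounding):

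| Scenario | u = 10% | u = 20% |
|---|---|---|
| A | +0.004 | +0.007 |
| B | +0.028 | +0.063 |
| C | −0.043 | −0.094 |

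Restricting the analysis can gain or lose power, and the loss under C exceeds the gain under A or B at the same share.

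**The case against.** The strongest reply is that the population is stated many times and that the word booster presupposes an earlier vaccination. The Intake Survey, scripts, manual and several figures, including one directly after the exclusion list, are not in the text and may contain a screen. This stands to the extent that nothing can be said about who was enrolled. A reader might infer that the trial did recruit never-vaccinated patients; the documents do not show that. They do show that the list presupposes earlier vaccination without requiring it, and leaves it undefined.

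The power figures are also open to challenge, and rightly. Section XVII gives 5% and the 7-point gain for whole arms. If those rates already describe the arms as enrolled, power is 0.800 whatever the mix. The loss of about 0.16 needs a 20% share and no messaging effect in that group, and the documents support neither.

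A reader might also take the wording in Section XVII to mean that the trial was sized for the wrong population. The same sentence speaks of booster uptake, the arithmetic reproduces without the word, and the 5% is tied to this trial's control arm. It is best read as a slip. Because no source is given for the 5%, one confirming sentence is still reasonable.

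**Conclusion.** The point holds for the written list: Section VIII does not require any COVID-19 vaccination before the index visit, while every aim is set in vaccinated ED patients. This is more than a missing detail, because following the list exactly could enrol people outside every aim and the plan has no later step to separate them.

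The numerical consequence is unknown and may be nil. The range of 0.800 to 0.643 for power at 248 per arm rests on assumed shares of up to 20%, on assumed uptake, on applying 5% vs 12% to the vaccinated only, and on the plan's own formula for individual randomisation.

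Three stronger readings are not supported. Nothing suggests bias between arms, since the same list applies on all study days. Nothing shows first doses being counted as boosters, since the outcome steps in Section XIII ask about a booster. And 248 per arm contains no arithmetic error. The change is worth making because it is cheap and settles whom the result describes; confidence is medium, given the material not available.

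**What to change.** 1. In Section VIII, add an inclusion criterion requiring COVID-19 vaccination before the index visit. Define it as at least one dose or as a completed initial series; the survey in the Overview used the latter.
2. Ask it alongside the self-report of recent vaccination that exclusion 5 implies. The section does not describe a screening question for that self-report, so the wording and place of both should be written down.
3. In Section XVII, change unvaccinated to vaccinated and confirm in one sentence that the 5% control rate refers to that population. The 248 per arm stays.
4. If enrolment has begun and prior vaccination was recorded, keep the intention-to-treat analysis of Section XV as primary. Report the vaccinated-only result, under the same definition, as a labelled supplementary analysis, and note that it may gain or lose power as shown above.

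The cost is one criterion, one screening question, one corrected word and one sentence, plus a protocol modification through the multi-site reliance arrangement in Section II and a short retraining note to five sites. The downside is a slightly smaller pool of eligible patients.
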